6. Subjects having on average ≥ 4 spontaneous and observable focal-onset seizures per 28 days (based on Investigator assessment of subject report) with at least 1 seizure during each 4-week interval of the 8-week retrospective Baseline Period prior to entry. Additionally, subjects must experience ≥ 4 spontaneous and observable focal-onset seizures per 28 days (based on Investigator assessment of subject report) during the 4-week Baseline Period.
7. Subject has failed to achieve seizure control with ≥ 4 tolerated and appropriately chosen prior AEDs, including past and ongoing treatment, that were individually optimized for adequate dose and duration. Prior discontinued AED treatment would need to be assessed by the Investigator considering the patient medical records and patient and/or caregiver interview. "Prior AED" is defined as all past and ongoing AED treatments with a start date before the Screening Visit (Visit 1).

Concomitant epilepsy treatment

8. Subject is currently treated with an individually optimized and stable dose of at least 1 and up to 3 AEDs for the 8 weeks prior to the Screening Visit (Visit 1) with or without additional concurrent vagus nerve stimulation (VNS) or other neurostimulation treatments. The latter will not be counted as AEDs for the purpose of eligibility.

Laboratory parameter

9. Subject has clinical laboratory test results within the reference ranges of the laboratory or isolated test results that are outside the specified ranges and that are deemed as not clinically significant by the Investigator.

Birth control

10. Female subjects of child bearing potential must have a negative serum pregnancy test at the Screening Visit (Visit 1), which is confirmed to be negative by urine testing prior to the first dose of IMP at Day 1 (Visit 2) and prior to further dispensing at each study visit thereafter. Subjects will be withdrawn from the study as soon as pregnancy is known.

Female subjects will use an efficient form of contraception for the duration of the study for a period of 3 months after their last intake of IMP. Hormonal contraception may be susceptible to an interaction with the IMP, which may reduce the efficacy of the contraception method. The potential for reduced efficacy of any hormonal contraception method requires that a barrier method (preferably male condom) also be used.

Birth control methods considered as an efficient form of contraception:

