## 10.2 Adverse events

Adverse events are recorded on the AE CRF as they occur, from the time informed consent is granted until study completion or study termination (end of the SFU period 30 days after the last IMP intake). All AEs will be coded using the latest available version of MedDRA.

A treatment-emergent adverse event (TEAE) is defined as any event not present prior to the initiation of the first dose of study treatment or any unresolved event already present before initiation of the first dose that worsens in intensity following exposure to the treatment. The number and percentage of subjects who experience TEAEs at any time during the study will be summarized by SOC and PT. The following tabular summaries will be presented for the SS:

- Incidence of pre-treatment AEs. Pre-treatment AEs are AEs with start dates prior to the date of first dose of IMP.
- Incidence of TEAEs during the Treatment Period – Overview. Of note, the corresponding table is required for data transparency reporting.
- Incidence of TEAEs by period (Treatment Period, Titration and Stabilization Period, Maintenance Period, Conversion Period, and Taper and SFU Period)
- Incidence of Serious TEAEs by period (Treatment Period, Titration and Stabilization Period, and Maintenance Period)
- Incidence of TEAEs leading to discontinuation by period (Treatment Period, Titration and Stabilization Period, and Maintenance Period)
- Incidence of TEAEs leading to dose reduction during the Stabilization Period

The following will be presented for TEAEs during the overall Treatment Period:

- Subject numbers for TEAEs
- Incidence of TEAEs occurring in at least 5% of subjects in any treatment group

- Incidence of TEAEs occurring in at least 2% of subjects in any PSL group and greater than placebo group
- Incidence of TEAEs by Relationship
- Incidence of TEAEs by Maximum Intensity
- Incidence of TEAEs of special interest
- Incidence of SAEs by Relationship. Of note, the corresponding table is required for data transparency reporting.
- Incidence of Fatal TEAEs by Relationship. Of note, the corresponding table is required for data transparency reporting.
- Incidence of Non-Serious TEAEs above the threshold of 5% of subjects in any treatment group. Of note, the corresponding table is required for data transparency reporting.

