### **10.3 Clinical laboratory evaluations**

Clinical laboratory hematology, chemistry and urinalysis measurements obtained from blood/urine samples collected throughout the study are presented in Table 10-1.

During the study, non-protocol-specified lab parameters (unplanned) may be collected. Summaries of lab parameters will only include planned parameters as specified in the protocol. All lab parameter values will be listed and summarized using international units.

The observed value and change from Baseline will be summarized descriptively by treatment group and PSL total group and scheduled study visit. The Last Visit, minimum, and maximum post-baseline values during the Treatment Period will also be included. These summaries will be organized by lab function panel and parameter.

Shift from Baseline to the maximum and minimal values during the Treatment Period based on normal range (Low, Normal, High) will be provided for hematology and blood chemistry parameters in Table 10-1.

Possibly clinically significant treatment-emergent (PCST) criteria have been developed based on FDA Division of Neuropharmacologic Drug Products guidelines with some UCB-defined additions and are provided in Appendix 13.1. For lab parameters with PCST criteria, the number and percentage of subjects with a PCST value at any time (scheduled and unscheduled visits) during the Treatment Period will be summarized by treatment group and PSL total group. . Treatment-emergent values are those occurring any time on or after the first dose of study medication in EP0091. Subject numbers for those meeting the PCST criteria will also be presented.

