### 13 APPENDICES

#### 13.1 PCST Criteria for Hematology, Serum Chemistry and Urinalysis Parameters

##### 13.1.1 Hematology

PARAMETER	AGE RANGE	UNIT (conventional)	ABNORMALITY CRITERIA (conventional)	UNIT (standard)	ABNORMALITY CRITERIA (standard)
Hematocrit	<2y	%	≤27 >45	%	≤27 >45
	2y - <18y		≤29 >47		≤29 >47
	≥18y		≤85% of LLN ≥115% of ULN		≤85% of LLN ≥115% of ULN
Hemoglobin	<2y	g/dL	≤9.0 >15.0	g/L	≤90 >150
	2y - <18y		≤9.5 >16.0		≤95 >160
	≥18y		≤85% of LLN ≥115% of ULN		≤85% of LLN ≥115% of ULN
WBC/Leukocytes	<12y	10  /L	<3.5 >15.0	G/L	<3.5 >15.0
	≥12y		<3.0 >12.0		<3.0 >12.0
Neutrophils Absolute	>1m	10  /L	<1.5	G/L	<1.5
Lymphocytes	<6m	%	≤30.0	%	≤30.0
	6m - <6y		≤22.0		≤22.0
	6y - <18y		≤12.0 ≥80.0		≤12.0 ≥80.0
	≥18y		≤10.0 ≥80.0		≤10.0 ≥80.0

PARAMETER	AGE RANGE	UNIT (conventional)	ABNORMALITY CRITERIA (conventional)	UNIT (standard)	ABNORMALITY CRITERIA (standard)
Basophils	>1m	%	≥3.0	%	≥3.0
Eosinophils	>1m	%	≥10.0	%	≥10.0
Monocytes	>1m	%	≥20.0	%	≥20.0
Platelets	>1m	10  /L	≤100 >600	G/L	≤100 >600
RBC/ Erythrocytes	<2y	10  /L	<3.0	TL	<3.0
	≥2y		<3.5		<3.5

Abbreviations: F=female; M=male; m=month; y= year. A month is defined as 30 days; a year is defined as 365.25 days.

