### 13.1.3 Urinalysis

Qualitative urine parameters are generally reported by a descriptive score, which differs among laboratories. For data analysis purpose, a four-point scale is used. Five-point, six- point, or seven-point scales will be collapsed into a four-point scale first. A value is considered possibly clinically significant treatment emergent abnormal if an upward shift of at least 2 degrees from the baseline occurs under investigational treatment. To collapse the results in a five-point scale into a four-point scale, the lowest two positive results will be combined (see example below). For results reported with a scale of more than five-point, please consult your study physician for how to collapse into four-point scale.

Original Five-point Scale	Four-point Scale
Negative/None	Negative/None
Trace/Rare/Mild/A Few	Trace/1+/Rare/Mild/A Few
1+	
2+/Mod	2+/Mod
3+/Sev	3+/Sev

This document cannot be used to support any marketing authorization application and any extensions or variations thereof.

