### 13.2 Abnormal Criteria for Vital Sign and Body Weight Parameters

Abnormality criteria to be applied in the assessment of vital signs parameter values are given below.

PARAMETER	AGE RANGE	ABNORMALITY CRITERIA
Pulse Rate (beats/minute)	<6m	<100 >180
	6m - <3y	<90 >150
	3y - <12y	<60 >130
	12y - <17y	<50 >120
	≥17y	<50 and a decrease from Baseline of ≥15 >120 and an increase from Baseline of ≥15
Systolic Blood Pressure (mmHg)	<6m	<60 >100
	6m - <3y	<70 >120
	3y - <12y	<80 >140
	12y - <17y	<90 >160
	≥17y	≤ 90 and a decrease from Baseline of ≥20 ≥ 180 and an increase from Baseline of ≥20
Diastolic Blood Pressure (mmHg)	<6m	<40 >65
	6m - <3y	<45 >75
	3y - <12y	<50 >80
	12y - <17y	<50 >105
	≥17y	<50 and a decrease from Baseline of ≥15 >105 and an increase from Baseline of ≥ 15
Respiratory Rate (breaths/minute)	<6m	<25 >55
	6m - <3y	<20 >45
	3y - <12y	<15 >35
	≥12y	<10 >25

PARAMETER	AGE RANGE	ABNORMALITY CRITERIA
Temperature	>1m	>101 °F (38.3°C)
Body Weight	1m - <17y	<3% or 97% of the normal body weight growth curve ranges based on gender and the age of subject on date of weight assessment a
	≥17y	≥ 10% change from Baseline (an increase or a decrease) a

Abbreviations: m = month, y = year. A month is defined as 30 days; a year is defined as 365.25 days. asource: <http://www.cdc.gov/growthcharts/>

This document cannot be used to support any marketing authorization application and any extension or variations thereof.

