### 13.3 Abnormal Criteria for ECG

Abnormality criteria to be applied in the assessment of ECG parameter values are given below:

Parameter	Age	Abnormality Criteria
QT interval (ms)	1m-<12y	>500
	>12y	>500 or ≥60ms increase from Baseline
QTc(F) (ms)	<6m	>490, or >15% increase from Baseline
	6m-<3y	>440, or >15% increase from Baseline
	3y-<12y	>440, or >15% increase from Baseline
	>12y- <17y	>440, or >15% increase from Baseline
	≥17y	>500 or ≥60ms increase from Baseline
QTc(B) (ms)	<6m	>490, or >15% increase from Baseline
	6m-<3y	>450, or >15% increase from Baseline
	3m-<12y	>450, or >15% increase from Baseline
	>12y- <17y	>450, or >15% increase from Baseline
	≥17y	>500 or ≥60ms increase from Baseline
PR interval (ms)	<6m	>150, or >25% increase from Baseline
	6m-<3y	>170, or >25% increase from Baseline
	3y-<12y	>180, or >25% increase from Baseline
	>12y - <17y	>200, or >25% increase from Baseline
	≥17y	Treatment-emergent value >200, >220, >250
QRS interval (ms)	<6m	>90, or >25% increase from Baseline
	6m-<3y	>90, or >25% increase from Baseline
	3y-<12y	>100, or >25% increase from Baseline
	>12y - <17y	>110, or >25% increase from Baseline
	≥17y	Treatment-emergent value >100, >120, >140
Heart rate (bpm)	<6m	<100, >180
	6m-<3y	<90, >150
	3y-<12y	<60, >130
	>12y	<50, >120

Abbreviations: bpm = beats per minute; m = months; ms = milliseconds; QTc = corrected QT interval; y = years. A month is defined as 30 days; a year is defined as 365.25 days. Note: Treatment-emergent is defined as meeting the criteria at any post-Baseline visit during the Treatment Period (including unscheduled visits) and not meeting the same criteria during Baseline

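### For hematology and serum chemistry, SAP 10.3 defines treatment-emergent by timing alone, so an abnormality already present at Baseline that persists is counted as emerging on treatment.

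*SAP*

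**What the plan says.** SAP 10.3 will summarize, by treatment group and for PSL total, "the number and percentage of subjects with a PCST value at any time (scheduled and unscheduled visits) during the Treatment Period". The term treatment-emergent is then defined: "Treatment-emergent values are those occurring any time on or after the first dose of study medication in EP0091". The limits are in Appendix 13.1. For adults, each hematology row (for example "Neutrophils Absolute", below 1.5 G/L) and each chemistry row is a threshold on the observed value, either a fixed number or a percentage of the normal limit. No row refers to Baseline.

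Other rules in the same SAP do look back:

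- Urinalysis PCST (13.1.3) requires that "an upward shift of at least 2 degrees from the baseline occurs under investigational treatment".
- A treatment-emergent adverse event (10.2) is "any event not present prior to the initiation of the first dose of study treatment", or an event already present that worsens.
- The note to the ECG criteria (13.3) defines treatment-emergent as meeting the criterion post-Baseline "and not meeting the same criteria during Baseline".
- Adult pulse and blood pressure limits (13.2) combine a level with a change, for example "<50 and a decrease from Baseline of ≥15".

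Protocol 13.4.1 also promises treatment-emergent laboratory abnormalities but does not define the term, so it does not fill the gap.

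**The concern.** The word emergent tells the reader that the abnormality appeared or worsened on treatment. Under the timing-only rule it can mean only that the abnormality was still there. Subjects can enter in that state: inclusion criterion 9 (Protocol 6.1) admits "isolated test results that are outside the specified ranges and that are deemed as not clinically significant by the Investigator", and exclusion criterion 3 (Protocol 6.2) sets numeric entry limits only for ALT, AST, ALP and bilirubin.

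At stake is the clarity of a descriptive safety table that serves the secondary objective of assessing safety relative to placebo. Some of the limits matter clinically. The PCST cut-offs for eosinophils (10% or more), neutrophils (below 1.5 G/L) and platelets (100 G/L or less) are the same values that Protocol 6.3 lists as treatment-emergent laboratory signs when a multiorgan hypersensitivity reaction is suspected.

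**Working it through.** **Step 1: which parameters are affected.** Appendix 13.1.1 lists 10 hematology parameters and 13.1.2 lists 23 chemistry parameters. None carries a Baseline term. SAP 10.3 limits summaries to planned parameters, so the lists must be matched to Table 10-1. All 10 hematology parameters are planned. Nine chemistry rows are not in the chemistry column: GGT, total protein, albumin, creatinine clearance, phosphorus, triglycerides, uric acid, thyroxine and globulin. That leaves 23 − 9 = 14 chemistry rows (BUN and urea counted separately), and 10 + 14 = 24 in all.

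**Step 2: follow one subject through the rule.** Suppose sodium is 129 mmol/L at Baseline, judged not clinically significant, and 129 mmol/L at Visit 4. The limit is 130 or below. The Visit 4 value falls after first dose and meets the limit, so the subject is counted as treatment-emergent although nothing changed. Under the 13.3 note, applied to the same data, the subject would not be counted.

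**Step 3: do other planned summaries correct the count?** The shift tables in 10.3 use Low, Normal and High, so a Low-to-Low subject is not identified as having met the PCST limit at Baseline. Change-from-Baseline summaries are group statistics. Listings and subject numbers allow tracing case by case but leave the table as it is.

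**Step 4: illustration of size.** The plan states no figure to reproduce, and the documents give no Baseline PCST rate. Let *c* be the share already beyond the limit at Baseline and still beyond it on treatment, and *p* the true emergent rate in the rest. Then:

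- counted rate = *c* + (1 − *c*)*p*
- counted difference = (1 − *c*)(*p*₁ − *p*₀)

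Assume *p*₀ = 2% on placebo and *p*₁ = 6% on PSL, with the planned 80 per arm (SAP 2.7). At *c* = 5%, the placebo rate is 0.05 + 0.95 × 0.02 = 6.9%, the PSL rate is 0.05 + 0.95 × 0.06 = 10.7%, the ratio is 10.7/6.9 = 1.55, and the difference is 0.95 × 4 = 3.8 points.

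| *c* (assumed) | Carried over per arm (80*c*) | Placebo | PSL | Ratio | Difference (points) |
|---|---|---|---|---|---|
| 0 | 0 | 2.0% | 6.0% | 3.00 | 4.0 |
| 1% | 0.8 | 3.0% | 6.9% | 2.33 | 4.0 |
| 3% | 2.4 | 4.9% | 8.8% | 1.79 | 3.9 |
| 5% | 4.0 | 6.9% | 10.7% | 1.55 | 3.8 |
| 10% | 8.0 | 11.8% | 15.4% | 1.31 | 3.6 |

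The percentages rise and the ratio shrinks markedly. The absolute difference barely moves.

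**The case against.** The strongest reply is that this is a descriptive table with no test attached, in a section that also plans change from Baseline, post-baseline extremes, shift tables and full listings. The laboratory variable is an other safety variable, not a primary one. Liver signals have their own tables in 10.3.1, and laboratory findings reported as adverse events fall under a definition that does look back. Entry screening also limits carry-over: criterion 9 accepts only isolated results, exclusion 10 removes conditions such as bone marrow depression or severe renal impairment that could impair reliable participation, and most PCST limits lie well outside the normal range. All of this stands, and it limits the consequence. None of it changes what the PCST table counts.

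A reader might also infer that laboratory tests are the SAP's lone exception to a uniform rule. The documents do not support that. In the adult ECG rows the term treatment-emergent appears only for PR and QRS; heart rate is a plain threshold, and the QT and QTc rows accept either an absolute value or an increase. Adult respiratory rate and temperature have no Baseline term, and neither do some of the liver criteria. The SAP mixes both kinds of limit. The narrower inconsistency remains: where the SAP defines treatment-emergent elsewhere, in 10.2 and in the 13.3 note, it requires that the finding was new or, for adverse events, new or worse.

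**Conclusion.** The point holds for hematology and serum chemistry, about 24 planned parameters. It does not hold for urinalysis. A stated rule, followed exactly, labels persisting pre-existing abnormalities as treatment-emergent. PCST percentages are inflated in every arm and PSL-to-placebo ratios are diluted.

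Three stronger readings are tempting and are not supported:

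- **Bias for or against PSL.** Carry-over precedes randomization, so it is balanced between arms in expectation. Chance imbalance adds noise only.
- **A large effect.** The rates and carry-over shares in the illustration are assumptions. They show direction, not size, and true carry-over for a given parameter may be close to zero.
- **Damage to the main laboratory analysis.** The SAP does not give this table that status, and neither the efficacy analysis nor the primary safety variables depend on it.

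It is a real but contained defect that should be corrected because the remedy is cheap and the label is otherwise wrong.

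**What to change.** Replace the definition in SAP 10.3 for hematology and serum chemistry. A PCST value counts as treatment-emergent only if the subject meets the Appendix 13.1 criterion at any post-Baseline time in the Treatment Period, scheduled or unscheduled, and did not meet the same criterion in the same direction at Baseline as defined in SAP 3.3.2. Use subjects not meeting that criterion at Baseline as the denominator. Show subjects who already met it at Baseline on a separate line, so that further worsening in them is not lost. State that urinalysis follows 13.1.3.

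The cost is one or two sentences in the SAP and a filter in the table program, using a Baseline value that is already defined. The small downside is that denominators will vary by parameter and must be printed.

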**Table 10–1: Laboratory measurements**

Hematology	Chemistry	Urinalysis
Basophils	ALP	Glucose
Eosinophils	ALT	pH
Hematocrit	AST	RBC
Hemoglobin	Bilirubin	Total protein
Lymphocytes	BUN or urea	WBC
MCH	Calcium	Microscopy (WBC, RBC, casts, crystals, bacteria) a
MCHC	Chloride	Other
MCV	Creatinine	FSH b
Monocytes	Glucose	
Neutrophils	HDL	
Platelet count	LDH	
RBC count	LDL	
WBC count	Magnesium	
	Potassium	
	Sodium	
	Total bilirubin	
	Total cholesterol	

ALP=alkaline phosphatase; ALT=alanine aminotransferase; AST=aspartate aminotransferase; BUN=blood urea nitrogen; HDL=high density lipoprotein; FSH=follicle stimulating hormone; LDH=lactate dehydrogenase; LDL=low density lipoprotein; MCH=mean corpuscular hemoglobin; MCHC=mean corpuscular hemoglobin concentration; MCV=mean corpuscular volume; RBC=red blood cell; WBC=white blood cell

a Microscopy will be performed only in case of abnormalities.

b Only applicable to postmenopausal women

### 10.3.1 Subjects with potential drug-induced liver injury (PDILI)

There are specific criteria described in the protocol Section 11 to evaluate subjects for potential drug-induced liver injury (PDILI). The evaluations required by protocol for PDILI subjects are collected on the following CRFs:

- Most Recent Study Medication Administration, for PDILI
- Laboratory Tests DILI
- Vital Signs DILI
- Hepatic Event Supplemental Medical History for PDILI
- Potential Hepato-Toxic Medications Inquiry for PDILI

- Symptoms of Hepatitis and Hypersensitivity for PDILI
- Lifestyle PDILI
- Family Medical History for PDILI

Listings will be prepared presenting subjects with PDILI data. A summary of number and percent of subjects meeting PDILI criteria (ALT, AST, total bilirubin, ALP, and presence of symptoms) during the Treatment Period (scheduled and unscheduled visits) will be provided following the UCB standard table shell for PDILI Data. Subjects who met these criteria will be listed.

ALT Criteria	AST Criteria	Total Bilirubin Criteria	ALP Criteria	Presence of Symptoms
≥3xULN	≥3xULN	≥2xULN	≥2xULN	NA
≥8xULN	≥8xULN	NA		NA
≥3xULN	≥3xULN	NA		Y
≥3xULN <-5xULN and ≥2x Baseline	≥3xULN <-5xULN and ≥2xBaseline	<2xULN		N
≥5xULN <-8xULN and ≥2x Baseline	≥5xULN <-8xULN and ≥2xBaseline	<2xULN		N
≥5xULN and ≥2xBaseline	≥5xULN and ≥2xBaseline	<2xULN		N

N=No; NA=Not Applicable; ULN= upper limit of normal; Y=Yes.

A summary table highlighting the potential cases of Hy's Law, within each treatment group will be presented. Hy's Law is defined as:

- AST ≥3xULN or ALT ≥3xULN and
- Total Bilirubin ≥2xULN

In order to meet the above criteria, a subject must experience the elevation in bilirubin and ALT or AST at the same visit. For example, a subject who experiences a ≥2 x ULN elevation of bilirubin at one visit and a 3 x ULN elevation in ALT (or AST) at a subsequent visit has not fulfilled the Hy's law criteria.

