6.3.1 Potential drug-induced liver injury IMP discontinuation criteria

Subjects with potential drug-induced liver injury (PDILI) must be assessed to determine if IMP must be discontinued. In addition, all concomitant medications and herbal supplements that are not medically necessary should also be discontinued.

The PDILI criteria below require immediate and permanent discontinuation of IMP:

- Subjects with either of the following:
 - ALT or AST $\geq 5\text{x ULN}$
 - ALT or AST $\geq 3\text{xULN}$ and coexisting total bilirubin $\geq 2\text{xULN}$

The PDILI criterion below requires immediate discontinuation of IMP:

- Subjects with ALT or AST $\geq 3\text{xULN}$ who exhibit temporally associated symptoms of hepatitis or hypersensitivity. Hepatitis symptoms include fatigue, nausea, vomiting, right upper quadrant pain or tenderness. Hypersensitivity symptoms include fever (without clear alternative cause), rash, or eosinophilia (ie, $>5\%$).

The PDILI criterion below allows for subjects to continue on IMP at the discretion of the Investigator:

- Subjects with ALT or AST $\geq 3\text{xULN}$ (and $\geq 2\text{x Baseline}$) and $< 5\text{xULN}$, total bilirubin $< 2\text{xULN}$, and no eosinophilia (ie, $\leq 5\%$), with no fever, rash, or symptoms of hepatitis (eg, fatigue, nausea, vomiting, right upper quadrant pain or tenderness).

Evaluation of PDILI must be initiated as described in [Section 11.2.1](#). If subjects are unable to comply with the applicable monitoring schedule, IMP must be discontinued immediately.

Investigators should attempt to obtain information on subjects in the case of IMP discontinuation to complete the final evaluation. Subjects with PDILI should not be withdrawn from the study until investigation and monitoring are complete. All results of these evaluations and observations, as well as the reason(s) for IMP discontinuation and subject withdrawal (if applicable), must be recorded in the source documents. The eCRF must document the primary reason for IMP discontinuation.

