11.1.1.2.2 Adverse events of special interest

Potential Hy's Law, defined as $\geq 3 \times \text{ULN}$ ALT or AST with coexisting $\geq 2 \times \text{ULN}$ total bilirubin in the absence of $\geq 2 \times \text{ULN}$ ALP, with no alternative explanation for the biochemical abnormality, must ALWAYS be reported to UCB as an AE of special interest (ie, without waiting for any additional etiologic investigations to have been concluded). Follow-up information should then be reported if an alternative etiology is identified during investigation and monitoring of the subject.

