- ^a Hepatitis symptoms include fatigue, nausea, vomiting, and right upper quadrant pain or tenderness; hypersensitivity symptoms include eosinophilia (>5%), rash, and fever (without clear alternative cause).
- ^b If the subject also has $\geq 2 \times$ ULN ALP, the possibility of an indication of biliary obstruction should be discussed with the Medical Monitor.
- ^c Details provided in [Section 11.2.1.1](#). The local hepatologist is the expert usually consulted by the treating physician for assessment and management of potential hepatic disease. This would usually be a hepatologist, but may be a gastroenterologist.
- ^d Unless an alternative monitoring schedule is agreed by the Investigator and UCB Study Physician. Determination of stabilization is at the discretion of the Investigator in consultation with the hepatologist (as applicable) and UCB Study Physician, as needed.

REDACTED COPY
This document cannot be used to support any marketing authorization application and any extensions or variations thereof.

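### Row 1 of the SAP's PDILI table adds an ALP ≥2xULN condition that the protocol criterion lacks, so some qualifying asymptomatic subjects would meet no row of that table

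*SAP*

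**What the plan says.** SAP 10.3.1 introduces a six-row criteria table by announcing "A summary of number and percent of subjects meeting PDILI criteria (ALT, AST, total bilirubin, ALP, and presence of symptoms"), so ALP is named in the running text as one of the criteria. In column order ALT, AST, total bilirubin, ALP, symptoms, row 1 reads "≥3xULN ≥3xULN ≥2xULN ≥2xULN NA". The ALP cell is blank in rows 2 to 6. Subjects meeting the criteria are also to be listed.

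Below the table, the same section plans a second display: "A summary table highlighting the potential cases of Hy's Law, within each treatment group will be presented". It requires AST or ALT ≥3xULN and total bilirubin ≥2xULN, and adds that "a subject must experience the elevation in bilirubin and ALT or AST at the same visit". ALP is not mentioned.

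The protocol states the matching PDILI criterion in Section 6.3.1 as ALT or AST ≥3xULN "and coexisting total bilirubin" ≥2xULN, and Table 11-3 repeats it. Neither sets an ALP condition. ALP enters through footnote b to Table 11-3, attached to the bilirubin cell: if the subject has ALP ≥2xULN as well, "the possibility of an indication of biliary obstruction should be discussed with the Medical Monitor". Section 11.1.1.2.2 defines potential Hy's Law with the same ALT/AST and bilirubin thresholds, but in the absence of ≥2xULN "ALP, with no alternative explanation for the biochemical abnormality".

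**The concern.** Row 1 of the SAP table is meant to reproduce a protocol criterion, yet as printed it is narrower. What the protocol treats as an additional finding to discuss has become a condition for being counted. It also runs opposite to the protocol's potential Hy's Law definition, which requires that finding to be absent.

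At stake is the by-arm n (%) of subjects meeting PDILI criteria and the listing that goes with it. A subject who met a Section 6.3.1 criterion could be missing from both. Protocol 11.2.1 treats potential Hy's Law as a kind of PDILI event, so a subject counted in the SAP's Hy's Law summary but in no PDILI row would be an internal contradiction in the safety report.

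**Working it through.** The plan gives no figure to reproduce, so the check is logical: which profiles meet which definition.

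Definitions applied:
- Protocol PDILI criterion (6.3.1, Table 11-3): ALT or AST ≥3xULN and bilirubin ≥2xULN, any ALP.
- SAP row 1 as printed: the same, and ALP ≥2xULN.
- SAP row 2: ALT/AST ≥8xULN. Row 3: ALT/AST ≥3xULN with symptoms. Rows 4 to 6: ALT/AST in the bands 3 to <5, 5 to <8 and ≥5xULN, each with at least 2x Baseline, bilirubin <2xULN and no symptoms.
- SAP Hy's Law summary: AST or ALT ≥3xULN and bilirubin ≥2xULN at the same visit.
- Protocol potential Hy's Law (biochemical part): as the PDILI criterion, with ALP <2xULN.

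Assumptions: columns within a row are joined by 'and', ALT and AST by 'or', values are concurrent, and ALT/AST is at least 2x Baseline.

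Grid: ALT/AST at 3.5, 6 and 9xULN; bilirubin at 1 and 2.5xULN; ALP at 1 and 2.5xULN; symptoms no or yes. That is 3 × 2 × 2 × 2 = 24 profiles.

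The protocol criterion is met by the 3 × 2 × 2 = 12 profiles with bilirubin 2.5xULN. Row 1 as printed counts the 6 with ALP 2.5xULN. The other 6 (bilirubin 2.5xULN, ALP 1xULN) fall out as follows:

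| ALT/AST (xULN) | Symptoms | PDILI rows met as printed | Rows met without ALP in row 1 | SAP Hy's Law summary |
|---|---|---|---|---|
| 3.5 | no | none | 1 | counted |
| 3.5 | yes | 3 | 1, 3 | counted |
| 6 | no | none | 1 | counted |
| 6 | yes | 3 | 1, 3 | counted |
| 9 | no | 2 | 1, 2 | counted |
| 9 | yes | 2, 3 | 1, 2, 3 | counted |

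So 4 of the 6 are recovered by rows 2 and 3, and 2 meet no row. Rows 4 to 6 cannot catch them because they require bilirubin <2xULN. The gap is therefore ALT/AST 3 to <8xULN, bilirubin ≥2xULN, ALP <2xULN, no symptoms. With the ALP condition removed, row 1 counts 12 of 12.

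The SAP Hy's Law summary counts all 12 qualifying profiles: the 6 above, which match the biochemical part of the protocol definition, and the 6 with ALP ≥2xULN, which that definition excludes.

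Scale: SAP 2.7 plans 80 subjects per arm, so one such subject would shift an arm's percentage by 1/80 = 1.25 points. The documents give no event rate, so this is the size of one case and not a forecast.

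**The case against.** The strongest reply is that nothing disappears. The Hy's Law summary in the same SAP section uses the thresholds row 1 should have used, without ALP, and reports by arm. Protocol 11.2.1 requires every PDILI event to be reported as an AE, and potential Hy's Law as an AE of special interest; SAP 10.2 tabulates TEAEs of special interest, and SAP 10.3.1 plans listings of PDILI data apart from the criteria table. This stands. It limits the point to a wrong count in one table and its criteria-based listing, and to a disagreement between two displays.

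A second reply is that the ALP entry may be a flag and not a condition. It sits in the row to which footnote b applies, and the ALP cells below it are blank where other cells that do not apply print NA. The table layout may have shifted when text was taken from the PDF, and the sponsor's standard table shell is not among the documents. The SAP also gives no rule for joining columns: if ALT and AST must be read as 'or' by reference to the protocol, ALP might be read through the protocol too. This lowers confidence but does not settle the matter, because the introductory sentence lists ALP as a criterion and no text calls it a flag.

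A reader might infer that the table counts only cholestatic cases and misses hepatocellular injury altogether. The documents do not support that. Rows 2 and 3 catch cases with ALT/AST ≥8xULN or with symptoms whatever the ALP, and footnote b speaks only of a possibility of biliary obstruction. The protocol's PDILI criterion applies at any ALP; only its Hy's Law definition excludes ALP ≥2xULN.

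**Conclusion.** The conflict holds within these limits. As printed, row 1 is narrower than the protocol criterion it stands for, and one defined group (asymptomatic, ALT/AST 3 to <8xULN, bilirubin ≥2xULN, ALP <2xULN) meets the protocol criterion but no row of the PDILI table. The same subjects would be counted in the Hy's Law summary when the elevations occur at one visit, so the effect is inconsistency between two planned displays and with the protocol, not loss of cases from reporting. That summary departs from Protocol 11.1.1.2.2 in the other direction by leaving out the requirement that ALP ≥2xULN be absent, so neither display isolates the protocol's group.

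The conclusion rests on applying the ALP column as a condition and on the table layout being faithful to the SAP; confidence is medium on that account. If ALT and AST were also joined by 'and', row 1 would be narrower still. The affected output is descriptive safety reporting; no efficacy inference, error rate or sample size is touched. A correction before programming is worthwhile because two programmers could produce different counts from the present wording.

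**What to change.** Reporting changes only, in SAP 10.3.1:

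- Remove ALP as a condition in row 1, so that the row matches Protocol Table 11-3: ALT or AST ≥3xULN and total bilirubin ≥2xULN.
- Show ALP <2xULN and ALP ≥2xULN as a descriptive split of that row, which keeps the footnote b information visible.
- State that the ALT and AST columns are joined by 'or'.
- Reconcile the Hy's Law summary with Protocol 11.1.1.2.2: either add the absence of ALP ≥2xULN, or say that the summary is deliberately broader and show the same ALP split.
- Check the sponsor's standard PDILI table shell against the corrected wording.

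The cost is a few lines of SAP text and one extra split in a display. ALP is already in the planned chemistry panel, so no new data are needed, and no rule for managing subjects changes.
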